### 3. PATIENT SELECTION

### 3.1 Eligibility Criteria

3.1.1 Patients must have histologically or cytologically confirmed adenocarcinoma of the prostate that is castration-resistant, defined as:

- A castrate serum testosterone level  $\leq 50$  ng/dL or 1.7 nmol/L
- Bilateral orchiectomy or maintenance on androgen ablation therapy with luteinizing hormone-releasing hormone (LHRH) or antiandrogen such as bicalutamide. Androgen deprivation therapy needs to be maintained throughout the study unless a patient has had orchiectomy by surgery.
- Serum PSA progression defined as two consecutive increases in PSA over a previous reference value, each measurement at least 1 week apart.

3.1.2 Progression after androgen receptor blockers (enzalutamide, apalutamide, or darolutamide) or androgen synthesis blockers (abiraterone acetate) or chemotherapy (docetaxel or cabazitaxel). There are no maximum number of prior therapies.

3.1.3 Progressive castration-resistant prostate cancer with two or more skeletal metastases identified by Tc-99m bone scintigraphy or prostate specific membrane antigen (PSMA) PET scan .

3.1.4 Patients must have self-reported moderate to severe pain at trial entry (baseline weekly average “worst pain in the past 24-hours” scores of  $\geq 4$  on an 11-point numeric rating scale [NRS], the Brief Pain Inventory – Short Form [BPI-SF] item #3 for worst pain).

3.1.5 Patients must either currently employ regular (not occasional) analgesic medication use for cancer-related bone pain or have undergone treatment with EBRT for bone pain within 4 weeks before starting study treatment.

3.1.6 Age  $\geq 18$  years. Children  $< 18$  years of age are excluded from the study as the prevalence of prostate cancer is extremely rare in this age group.

3.1.7 Patients must have a life expectancy  $\geq 3$  months.

3.1.8 ECOG performance status  $\leq 2$  (Karnofsky  $\geq 60\%$ , see Appendix A).

3.1.9 Patients must have a serum PSA value  $\geq 1$  ng/mL.

3.1.10 Patients must have adequate organ and marrow function as defined below to be eligible for the first treatment administration:

– absolute neutrophil count	$\geq 1,000/\text{mcL}$
– platelets	$\geq 100,000/\text{mcL}$
– hemoglobin	$> 10.0 \text{ g/dL}$
– total bilirubin	$\leq 2.5 \times$ institutional upper limit of normal (ULN)
– AST(SGOT)/ALT(SGPT)	$\leq 5 \times$ institutional ULN
– creatinine	$\leq 1.7 \text{ mg/dL}$

OR

- glomerular filtration rate (GFR)  $\geq 50$  mL/min/1.73 m^2 (see Appendix B)

- 3.1.11 Patients receiving bisphosphonates or denosumab prior to enrollment can maintain therapy throughout all or part of the study. The bisphosphonate may be stopped or started at the discretion of the investigator throughout the study (*i.e.*, both treatment phase and follow-up). Injection of bisphosphonates should be done at least 2 hours before or after study drug administration.
- 3.1.12 Human immunodeficiency virus (HIV)-infected patients on effective anti-retroviral therapy with undetectable viral load within 6 months are eligible for this trial.
- 3.1.13 For patients with evidence of chronic hepatitis B virus (HBV) infection, the HBV viral load must be undetectable on suppressive therapy, if indicated.
- 3.1.14 Patients with a history of hepatitis C virus (HCV) infection must have been treated and cured. For patients with HCV infection who are currently on treatment, they are eligible if they have an undetectable HCV viral load.
- 3.1.15 Patients with a prior or concurrent malignancy whose natural history or treatment does not have the potential to interfere with the safety or efficacy assessment of the investigational regimen are eligible for this trial.
- 3.1.16 Patients with known history or current symptoms of cardiac disease, or history of treatment with cardiotoxic agents, should have a clinical risk assessment of cardiac function using the New York Heart Association Functional Classification. To be eligible for this trial, patients should be class 2B or better.
- 3.1.17 The effects of Sn-117m-DTPA on the developing human fetus are unknown. For this reason and because radionuclides are known to be teratogenic, male participants and their female partners must agree to use adequate contraception (hormonal or barrier method of birth control; abstinence) prior to study entry and for the duration of study participation. Should a woman become pregnant or suspect she is pregnant while her male partner is participating in this study, she should inform her treating physician immediately. Men treated or enrolled on this protocol must also agree to use adequate contraception prior to the study, for the duration of study participation, and 6 months after completion of Sn-117m-DTPA administration.
- 3.1.18 Patients must be willing and able to comply with the protocol and agree to return to the hospital for follow-up visits and examinations.
- 3.1.19 Ability to understand and the willingness to sign a written informed consent document.

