## 3.2 Exclusion Criteria

- 3.2.1 Patients must not have visceral metastases (such as liver and lung) as assessed by

abdominal/pelvic CT or chest X-ray within 12 weeks before starting study treatment.

- 3.2.2 Patients must not have malignant lymphadenopathy exceeding 3 cm in short-axis diameter.
- 3.2.3 Patients must not have imminent or established spinal cord compression based on clinical findings and/or MRI.
- 3.2.4 Patients who have had chemotherapy, immunotherapy, or external radiotherapy within 4 weeks prior to entering the study.
- 3.2.5 Patients must not have received systemic radiotherapy with radium-223, strontium-89, samarium-153, rhenium-186, or rhenium-188 for the treatment of bony metastases within 24 weeks before starting study treatment.
- 3.2.6 Patients who have not recovered from adverse events due to prior anti-cancer therapy (*i.e.*, have residual toxicities > Grade 1) with the exception of alopecia.
- 3.2.7 Patients must not have received any investigational agents within 4 weeks before starting study treatment, nor be scheduled to receive one during the planned treatment period.
- 3.2.8 Patients must not have unmanageable urinary incontinence.
- 3.2.9 Patients must not have had known non-pathological bone fractures within 2 months before starting study treatment.
- 3.2.10 Patients must not have a history of allergic reactions attributed to compounds of similar chemical or biologic composition to Sn-117m-DTPA.
- 3.2.11 Patients must not have uncontrolled intercurrent illness, including:
  - Any uncontrolled infection
  - Grade 2 or greater motor or sensory neuropathy
- 3.2.12 Patients with psychiatric illness/social situations that would limit compliance with study requirements.

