### **4.3 Patient Registration**

#### **4.3.1 OPEN / IWRS**

The Oncology Patient Enrollment Network (OPEN) is a web-based registration system available on a 24/7 basis. OPEN is integrated with CTSU regulatory and roster data and with the LPOs registration/randomization systems or the Theradex Interactive Web Response System (IWRS) for retrieval of patient registration/randomization assignment. OPEN or IWRS will populate the patient enrollment data in NCI's clinical data management system, Medidata Rave.

Requirements for OPEN access:

- A valid CTEP-IAM account.
- To perform enrollments or request slot reservations: Must be on an LPO roster, ETCTN corresponding roster, or PO roster with the role of Registrar. Registrars must hold a minimum of an Associate Plus (AP) registration type.
- If a DTL is required for the study, the registrar must hold the OPEN Registrar task on the DTL for the site.
- Have an approved site registration for the protocol prior to patient enrollment.

To assign an Investigator (IVR) or Non-Physician Investigator (NPIVR) as the treating, crediting, consenting, drug shipment (IVR only), or receiving investigator for a patient transfer in OPEN, the IVR or NPIVR must list the IRB number used on the site's IRB approval on their Form FDA 1572 in RCR. If a DTL is required for the study, the IVR or NPIVR must be assigned the appropriate OPEN-related tasks on the DTL.

Prior to accessing OPEN, site staff should verify the following:

- Patient has met all eligibility criteria within the protocol stated timeframes, and
- All patients have signed an appropriate consent form and HIPAA authorization form (if applicable).

Note: The OPEN system will provide the site with a printable confirmation of registration and treatment information. The IWRS system also sends an email confirmation of the registration. You may print this confirmation for your records.

Access OPEN at <https://open.ctsu.org> or from the OPEN link on the CTSU members' website. Further instructional information is in the OPEN section of the CTSU website at <https://www.ctsu.org> or <https://open.ctsu.org>. For any additional questions, contact the CTSU Help Desk at [name] or [[contact]](mailto:[contact]).

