**Patient Cloud**

#### **4.4 General Guidelines**

Following registration, patients should begin protocol treatment within 30 days. Issues that would cause treatment delays should be discussed with the Principal Investigator. If a patient does not receive protocol therapy following registration, the patient's registration on the study may be canceled. The Study Coordinator should be notified of cancellations as soon as possible.

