### 5.10.2.2.2 Timing of Assessment

Pain at baseline and analgesic use (pre-treatment, Week 0) will be measured via serial (daily) assessments in a 7-day run-in period. Patients will be considered evaluable if they complete assessments on  $\geq 4$  days within the 7-day run-in period. During treatment, pain and analgesic use will be measured every 2 weeks through Week 28, followed by routine clinic follow-up until 1 year or when patients experience new pain. Complete pain assessments via the full BPI-SF (Appendix D) will be collected at baseline, after Cycle 1, after Cycle 2, and at Week 28. Pain assessments will be halted at the patient's request or if the patient discontinues study treatment for reasons other than disease progression.

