#### 5.10.2.3.2 Timing of Recording

- The pain score and analgesic data will be assessed for inclusion determination during the pre-screening period within 2 weeks of a patient's enrollment.

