## 6.3 General Concomitant Medication and Supportive Care Guidelines

### 6.3.1 Concomitant Prostate Cancer Therapy

- Patients receiving bisphosphonates or denosumab prior to enrollment can maintain therapy throughout all or part of the study. The bisphosphonate may be stopped or

started at the discretion of the investigator throughout the study (*i.e.*, both treatment phase and follow-up). Injection of bisphosphonates should be done at least 2 hours before or after study drug administration.

- Patients who have not undergone bilateral orchiectomy are allowed and should receive LHRH agonists or antiandrogen such as bicalutamide throughout the study (*i.e.*, both treatment phase and follow-up).
- Cytotoxic chemotherapy, androgen receptor blockers, androgen biosynthesis inhibitors, other systemic radioisotopes, hemi-body external radiotherapy, and other investigational drugs should not be used during the treatment period. These treatments can be given if at least 8 weeks after the last injection.
- Colony stimulating factors (*e.g.*, erythropoietin and granulocyte colony stimulating factors) and transfusions products (*e.g.*, red blood cell transfusion, and/or platelet transfusion) as dictated by standard practice are acceptable while the subject is enrolled in the study.

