### 9. STATISTICAL CONSIDERATIONS

#### 9.1 Study Design/Endpoints

This is a single-arm, open-label phase 2 study to evaluate the efficacy of Sn-117m-DTPA on

sustained pain response in patients with CRPC metastatic to at least two bone sites, with at least one clinically meaningful pain at baseline ( $\geq 4$  on an 11-point pain intensity scale). Sustained pain-response is defined as: 1) achieving pain index  $\leq 3$  within a 12-week period and 2) maintaining that pain index  $\leq 3$  over a 16-week time period (beginning when the pain index  $\leq 3$  is initially achieved). The maximum duration of follow-up required to declare a patient a responder is 28 weeks, representing a patient who initially achieves pain index  $\leq 3$  toward the end of the 12-week period and is followed for an additional 16 weeks to confirm maintenance of pain index  $\leq 3$ .

Eligible patients will be assigned to receive Sn-117m-DTPA at 20 mCi/70 kg (0.28 mCi/kg) every 8 weeks for two cycles. Treatment will last for 16 weeks with two treatment injections given at 8-week intervals. The study utilizes a mini-max Simon two-stage design to assess anti-tumor activity and pain benefit of Sn-117m-DTPA.

Patients are not allowed to receive external radiation within 12 weeks from the start of treatment administration. If their pain index does not reach  $\leq 3$  after 12 weeks, they are not meeting the primary endpoint, and they can then get external radiation for pain control.

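### Criteria 3.1.5 and 3.2.4 conflict on recent external radiotherapy, and no rule says how radiotherapy shortly before the first injection is scored in the primary pain endpoint

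*Combined protocol and SAP*

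**What the plan says.** **Eligibility.** Section 3.1.5 gives two alternative ways to qualify: current regular analgesic use for cancer-related bone pain, "or have undergone treatment with EBRT for bone pain within 4 weeks before starting study treatment". Section 3.2.4 excludes "Patients who have had chemotherapy, immunotherapy, or external radiotherapy within 4 weeks prior to entering the study". Section 4.3.1 has site staff verify before opening the registration system: "Patient has met all eligibility criteria within the protocol stated timeframes".

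**Time to first dose.** Section 4.4: "Following registration, patients should begin protocol treatment within 30 days".

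**Radiotherapy on study.** Section 9.1: "Patients are not allowed to receive external radiation within 12 weeks from the start of treatment administration". Section 6.3.1 lists what is barred; the only external radiotherapy it names is in "hemi-body external radiotherapy, and other investigational drugs should not be used during the treatment period". Section 6.1 bars therapies outside 6.1 and 6.3 if they are given to treat the malignancy.

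**Baseline and endpoint.** Under 5.10.2.2.2, pre-treatment (Week 0) pain and analgesic use "will be measured via serial (daily) assessments in a 7-day run-in period". Under 5.10.2.3.2, the pain and analgesic data are "assessed for inclusion determination during the pre-screening period within 2 weeks of a patient's enrollment". The pain index in 5.10.2.2.1 combines percentage change in pain from baseline with analgesic intake. The primary endpoint needs an index of 3 or less by week 12, held for 16 weeks.

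**The concern.** The two criteria treat the same exposure in opposite ways and count from different dates. Sites may therefore screen differently, and the protocol does not say which criterion prevails.

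The second issue is attribution. There is no control arm, and the 10% null in 9.1 is set for patients without effective therapy. Palliative EBRT is given to relieve the pain that the endpoint measures. If it is given close to the first injection, relief that emerges after the baseline diary falls inside the 12-week onset window and looks like drug response. Neither 9.1 nor 9.6.2 has a non-responder, exclusion or sensitivity rule for EBRT before the first injection.

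The plan is also uneven: 9.4.3 counts first EBRT for skeletal symptoms as an event timed from enrolment, so the same treatment can be a skeletal event and leave the primary endpoint untouched.

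**Working it through.** **1. The two windows together.** Let E be the EBRT date, R registration and D the first injection, with R on or before D.

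- 3.1.5 (EBRT route): D − E ≤ 28 days.
- 3.2.4, reading entry as R: EBRT before registration is acceptable only if R − E > 28 days.
- For E before R, R − E ≤ D − E ≤ 28, so both cannot hold. The EBRT route is empty.
- If entry means D, the criteria are opposites over the same 28 days. The route is again empty.

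**2. The interval between R and D.** Reading entry as R, 3.2.4 looks back from R, and the 9.1 ban starts at D. Section 4.4 allows D − R up to 30 days. An interval is normal: the order form in Appendix L asks for the study ID assigned at registration and must go in at least a week before administration. Section 6.3.1 names only hemi-body radiotherapy, during the treatment period. Section 6.1 is arguable for palliative EBRT before dosing.

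**3. Direction of the bias (illustrative scores, not from the documents).** An index of 3 needs a fall of more than 33% with analgesics stable or reduced.

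- Diary before EBRT, baseline 7: EBRT alone takes pain to 4, a fall of 3/7 = 43%. If held, this is a response with no drug effect.
- Diary after EBRT has taken pain from 7 to 5: the score must now be below 5 × 0.67 = 3.35, so 3 or less. From a baseline of 7 it would have been below 7 × 0.67 = 4.69, so 4 or less. Response is harder to show.

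**4. The plan's own figures.** Section 9.1 states 10 then 15 patients, stopping at 1 or fewer of 10, success at 6 or more of 25, type I error 3.28%, power 80.17%, and about 55% early stopping under the null.

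P(success | p) = Σ over x = 2..10 of C(10,x) pˣ(1−p)¹⁰⁻ˣ · P(Bin(15,p) ≥ 6−x)

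| First stage | Type I error (p=0.10) | Power (p=0.30) | Early stop (p=0.10) |
|---|---|---|---|
| 10, as written | 2.77% | 74.0% | 73.6% |
| 15 | 3.28% | 80.17% | 54.9% |

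The stated figures belong to a first stage of 15. That is a separate defect; here it only means that both splits are shown.

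**5. Possible inflation.** Assume an inactive drug, a share f of patients exposed to EBRT, and sustained response q among them. The documents give neither f nor q. The response rate is p = 0.10(1−f) + qf. For f = 0.20 and q = 0.50, p = 0.08 + 0.10 = 0.18.

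Probability of a false success, 10+15 split (15+10 in brackets); with f = 0 it is 2.8% (3.3%):

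| Exposed | q=0.2 | q=0.3 | q=0.4 | q=0.5 |
|---|---|---|---|---|
| 1 of 25 (4%) | 3.3% (3.9%) | 3.9% (4.5%) | 4.5% (5.3%) | 5.2% (6.1%) |
| 3 of 25 (12%) | 4.5% (5.3%) | 6.8% (7.9%) | 9.6% (11.2%) | 13.1% (15.2%) |
| 5 of 25 (20%) | 5.9% (7.0%) | 10.7% (12.5%) | 17.0% (19.7%) | 24.7% (28.4%) |

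The nominal 5% level is passed once the no-drug response rate reaches about 11.6% (10+15) or 11.1% (15+10).

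**The case against.** A reader might infer that the conflict by itself lets recently irradiated patients in. It does not. Section 4.3.1 requires every criterion to be met, so the literal result is a dead clause. Exposure needs a site to breach 3.2.4 or EBRT after registration. A breach might be removed as a major violation under 9.6.2, although 9.1 keeps everyone who received any drug in the denominator and neither section names this case.

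A reader might also infer that EBRT between registration and the first injection breaks no rule. That is too strong: 6.1 could be read to cover it, and study entry in 3.2.4 is undefined. If entry means the start of treatment, 3.2.4 covers the interval and only the contradiction is left.

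On bias, 5.10.2.2.2 places the diary at Week 0, and note c of the study calendar requires it before treatment starts. A diary just before dosing would follow most EBRT given in the interval, so relief already obtained would lower baseline. The 16-week maintenance requirement also filters out short-lived relief. These points stand, and they leave the net direction uncertain. But 5.10.2.3.2 allows the inclusion ratings to come from pre-screening, and no section ties the diary used for the index to the days ending at the first injection. Inflation remains possible.

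On size, the inputs are assumed. With 10% exposed and 20% responding, p = 0.09 + 0.02 = 0.11 and the false-positive rate is 4.2% (10+15) or 4.9% (15+10), both under 5%.

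**Conclusion.** The contradiction between 3.1.5 and 3.2.4 is literal and holds whichever date study entry means. The missing scoring rule for EBRT before the first injection is also real. Both should be fixed.

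The effect on the primary result cannot be fixed from the documents. With an inactive drug, 4-20% of patients exposed and 20-50% sustained response among them, the false-positive rate of the written design moves from 2.8% to about 3-25%. This range covers only the inflating direction, where relief follows the diary; relief before the diary works against the drug.

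A reader might infer that the type I error is badly inflated. With 30% exposed and 50% responding, p = 0.07 + 0.15 = 0.22 and the rate is 42% (10+15) or 48% (15+10). The documents do not support that reading: it needs 7 or 8 of 25 patients to be irradiated through a route that is empty on paper or in an interval of at most 30 days, and a response rate in them above the 30% that the trial targets for the drug.

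**What to change.** 1. Reconcile 3.1.5, 3.2.4 and 9.1 to one stated reference date and define study entry. Which radiotherapy window applies is the sponsor's decision.
2. Record the date of last EBRT for every patient.
3. State in 9.1 that a patient given EBRT for bone pain between the start of the baseline diary used for the pain index and the first injection is a non-responder in the primary analysis. Say which 7-day diary that is. Simply requiring one diary that ends at the first injection would not work: it could not also establish 3.1.4 before registration, or before the dose is ordered a week ahead.
4. Add a sensitivity analysis that excludes patients irradiated in the 4 weeks before the first injection.

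The cost is amendment wording and one extra date on the case report form. The observed response rate may be slightly lower.

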## 3.2 Exclusion Criteria

- 3.2.1 Patients must not have visceral metastases (such as liver and lung) as assessed by

abdominal/pelvic CT or chest X-ray within 12 weeks before starting study treatment.

- 3.2.2 Patients must not have malignant lymphadenopathy exceeding 3 cm in short-axis diameter.
- 3.2.3 Patients must not have imminent or established spinal cord compression based on clinical findings and/or MRI.
- 3.2.4 Patients who have had chemotherapy, immunotherapy, or external radiotherapy within 4 weeks prior to entering the study.
- 3.2.5 Patients must not have received systemic radiotherapy with radium-223, strontium-89, samarium-153, rhenium-186, or rhenium-188 for the treatment of bony metastases within 24 weeks before starting study treatment.
- 3.2.6 Patients who have not recovered from adverse events due to prior anti-cancer therapy (*i.e.*, have residual toxicities > Grade 1) with the exception of alopecia.
- 3.2.7 Patients must not have received any investigational agents within 4 weeks before starting study treatment, nor be scheduled to receive one during the planned treatment period.
- 3.2.8 Patients must not have unmanageable urinary incontinence.
- 3.2.9 Patients must not have had known non-pathological bone fractures within 2 months before starting study treatment.
- 3.2.10 Patients must not have a history of allergic reactions attributed to compounds of similar chemical or biologic composition to Sn-117m-DTPA.
- 3.2.11 Patients must not have uncontrolled intercurrent illness, including:
  - Any uncontrolled infection
  - Grade 2 or greater motor or sensory neuropathy
- 3.2.12 Patients with psychiatric illness/social situations that would limit compliance with study requirements.

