## 6. TREATMENT PLAN

### 6.1 Agent Administration

Treatment will be administered on an outpatient basis. Reported adverse events and potential risks are described in Section 10. Appropriate dose modifications are described in Section 7. No investigational or commercial agents or therapies other than those described in Sections 6.1 and 6.3 may be administered with the intent to treat the patient's malignancy.

Study Regimen Description				
Agent	Dose	Route	Schedule	Cycle Length
Sn-117m-DTPA	20 mCi/70 kg (0.28 mCi/kg)	Slow IV injection over 10 min	Day 1	8 weeks*

\*Treatment continues for 2 cycles.

**Retreatment** after 2 cycles is allowed after an evaluation of AEs if:

- pain ( $\geq 4$  on 11-point intensity scale) recurs within 6 months after a 16-week pain observation period  
AND
- no disease progression on bone scans ( $\leq 2$  new bone lesions), or evidence of clinical progression (such as development of cancer-related symptoms)

Patients will be administered two additional cycles (8 weeks apart) if they meet the retreatment criteria. The maximum treatment dose per patient is four injections in this study.

Patients will be instructed to maintain a high fluid intake (drink at least two to three quarts of fluid every 24 hours) for 2 weeks after each Sn-117m-DTPA treatment to minimize a concentrated radioactive excretion. In general, drinking alcoholic beverages should be kept to a minimum or avoided completely. Patients will be educated on hygiene instruction/precautions on post-therapy treatment (see Appendix I).

Required Criteria for Each Re-Treatment:

Patients must have adequate organ and marrow function as defined below to be eligible for subsequent treatments after the first treatment administration:

- leukocytes	$\geq 2,000/\text{mcL}$
- absolute neutrophil count	$\geq 1,000/\text{mcL}$
- platelets	$\geq 75,000/\text{mcL}$
- hemoglobin	$\geq 8.0 \text{ g/dL}$
- total bilirubin	$\leq 2.5 \times \text{institutional ULN}$
- AST(SGOT)/ALT(SGPT)	$\leq 5 \times \text{institutional ULN}$
- creatinine*	$\leq 1.7 \text{ mg/dL}$
	OR
- glomerular filtration rate (GFR)	$\geq 50 \text{ mL/min}/1.73 \text{ m}^2$ (see Appendix B)

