## 11. STUDY CALENDAR

Baseline evaluations are to be conducted within 4 weeks prior to start of protocol therapy. Scans and x-rays must be done  $\leq$  8 weeks prior to the start of therapy. In the event that the patient's condition is deteriorating, laboratory evaluations should be repeated within 48 hours prior to initiation of the next cycle of therapy.

Visit dates and scans can be within  $\pm$  7 days of planned dates. Study treatment must start within 30 days of registration.

	Pre-study	Cycle 1 (8 weeks or 56 days)					Cycle 2 (8 weeks or 56 days)					Post-treatment					Follow-up a	Off-study visit	
		W1	W2	W4	W6	W8	W1	W2	W4	W6	W8	18 weeks	20 weeks	22 weeks	24 weeks	26 weeks	28 weeks		
Sn-117m-DTPA		A					A											A*	
Informed consent	X																		
Demographics	X																		
Medical History	X																		
Pain medication**	X	X	X	X	X	X		X	X	X	X		X		X		X	X (every 3 months)	X
Physical Exam	X	X		X	X			X		X		X		X		X		X	X
Vital signs	X	X		X	X			X		X		X		X		X		X	X
Height	X																		
Weight	X	X		X	X			X		X		X		X		X		X	X
Performance status	X																	X	
CBC/diff, platelets	X	X	X	X	X	X i		X	X	X	X		X		X		X	X	X
Serum chemistry b	X	X	X	X	X	X i		X	X	X	X		X		X		X	X	X
PSA	X			X	X			X		X		X		X		X		X	X
Adverse Events		X-----X																	
Patient-reported pain intensity scale and analgesic use c	X		X	X	X	X		X	X	X	X	X	X	X	X	X	X	X	X
Patient-reported CTCAE d			X	X	X	X		X	X	X	X	X	X	X	X	X	X	X	X
Sn-117m-DTPA dosimetry (optional) e		X	X	X	X														
Urine collection for urinalysis f	X						X												

NCI Protocol #: 10437  
 Version Date: January 10, 2022

	Pre-study	Cycle 1 (8 weeks or 56 days)					Cycle 2 (8 weeks or 56 days)					Post-treatment					Follow-up a	Off-study visit	
		W1	W2	W4	W6	W8	W1	W2	W4	W6	W8	18 weeks	20 weeks	22 weeks	24 weeks	26 weeks	28 weeks		
Radiologic evaluation (CT of abdomen/pelvis and bone scan) and chest X-ray g or PSMA PET CT scan	X					X					X				X			X (every 3 months)	
Research blood for genomic whole exome sequencing (mandatory when archival tissue or slides are submitted)	X																		
Research blood for exploratory studies (optional) h	X					X h					X h				X				
Archival tissue for genomic sequencing and exploratory PLK1 stain (optional)	X																		

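### The 24-week radioisotope exclusion in 3.2.5 covers five named isotopes only; any other therapeutic isotope needs 4 weeks off if investigational and has no stated interval if marketed

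*Combined protocol and SAP*

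**What the plan says.** Section 6.3.1 lists treatments that may not be given on study. After cytotoxic chemotherapy it names "androgen receptor blockers, androgen biosynthesis inhibitors, other systemic radioisotopes, hemi-body external radiotherapy, and other investigational drugs should not be used during the treatment period", and it allows them again from 8 weeks after the last injection. Section 6.1 adds a general bar: "No investigational or commercial agents or therapies other than those described in Sections 6.1 and 6.3 may be administered with the intent to treat" the cancer.

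Three exclusion criteria put a time limit on earlier anticancer therapy.
- 3.2.4 covers "chemotherapy, immunotherapy, or external radiotherapy within 4 weeks prior to entering the study".
- 3.2.5 covers systemic radiotherapy with "radium-223, strontium-89, samarium-153, rhenium-186, or rhenium-188 for the treatment of bony metastases within 24 weeks before starting study treatment".
- 3.2.7 reads "Patients must not have received any investigational agents within 4 weeks before starting study treatment".

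Criterion 3.1.2 requires progression after an androgen receptor blocker (enzalutamide, apalutamide or darolutamide), abiraterone, or a taxane. It does not say that the drug must have been stopped, or when.

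On baseline timing, section 5.10.2.2.2 says "Pain at baseline and analgesic use (pre-treatment, Week 0) will be measured via serial (daily) assessments in a 7-day run-in period". Section 11 says "Baseline evaluations are to be conducted within 4 weeks prior to start of protocol therapy"; those evaluations include PSA and, within serum chemistry, ALP.

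**The concern.** The sponsor set 24 weeks for earlier therapeutic isotopes but tied it to a closed list and to one indication. During treatment the rule is open-ended and takes in every other systemic radioisotope. A patient who has had an isotope outside the list can therefore enter much sooner, although the on-study ban treats that isotope in the same way as the five.

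What is at stake is mainly the patient's bone marrow. Section 2.1.3 identifies marrow toxicity as what chiefly limits the dose of the beta- and alpha-emitting bone-seeking agents. A short or absent interval could stack one marrow exposure on another.

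The secondary point concerns the baseline. The trial has a single arm, and the pain index (5.10.2.2.1) and the PSA and ALP responses (9.4.6) all score change from baseline. If a patient takes abiraterone, say, through the diary week and stops it at the first injection, baseline is on drug and follow-up is off drug. Any effect of stopping cannot then be separated from the effect of Sn-117m-DTPA.

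**Working it through.** The plan states no figure on this point, so the check sets the on-treatment ban beside the entry rules.

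| Class barred by 6.3.1 | Entry interval | Source |
|---|---|---|
| Cytotoxic chemotherapy | 4 weeks | 3.2.4 |
| Androgen receptor blockers | none if marketed | no criterion |
| Androgen biosynthesis inhibitors | none if marketed | no criterion |
| Other systemic radioisotopes | 24 weeks, five named isotopes for bony metastases | 3.2.5 |
| Hemi-body external radiotherapy | 4 weeks | 3.2.4 |
| Other investigational drugs | 4 weeks | 3.2.7 |

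Of the six classes, three have an interval, two have none and one is covered in part.

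**Isotopes.** Take a therapeutic isotope that is not among the five.
1. 3.2.5 does not apply, because its list is closed.
2. 3.2.4 does not apply, because its radiotherapy limb is confined to external treatment.
3. If the isotope is investigational, 3.2.7 applies and asks for 4 weeks. That is 24 − 4 = 20 weeks less than for a listed isotope.
4. If it is marketed, no criterion states an interval.
5. Two other criteria still act. 3.1.10 requires neutrophils of at least 1,000/mcL, platelets of at least 100,000/mcL and hemoglobin above 10.0 g/dL. 3.2.6 excludes residual toxicity above Grade 1, alopecia aside. Both describe the patient's state at entry; neither sets a time since the isotope.

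**Hormonal agents.** Take a patient on marketed enzalutamide, apalutamide, darolutamide or abiraterone at screening.
1. None of 3.2.4, 3.2.5 and 3.2.7 covers a marketed hormonal agent.
2. The alternatives in 3.1.2 are joined by *or*. A patient who qualifies through docetaxel may still be taking abiraterone.
3. The bans in 6.1 and 6.3.1 govern the treatment period. Stopping at the first injection complies with both.
4. The diary week and the baseline PSA/ALP come before that injection, the latter by up to 4 weeks. They may therefore be on drug.

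Antiandrogen such as bicalutamide, kept as androgen deprivation under 3.1.1 and 6.3.1, is expressly allowed and is not part of the gap.

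**The case against.** The strongest reply is that the consequence is small. Nothing in the documents says that an on-treatment ban must be mirrored by a washout; 3.2.4 itself lists immunotherapy, which 6.3.1 does not name. That is fair, and the mismatch alone is not the defect. What stands is that the protocol chose 24 weeks for earlier therapeutic isotopes and worded the rule so that others escape it.

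A reader might infer that earlier Sn-117m-DTPA is the telling case, since 4 weeks is about two half-lives and shorter than the protocol's own 8-week dosing interval. The documents do not support building on this.
- They point to no current source of patients dosed 4 to 24 weeks before entry. Section 2.2 counts 107 patients in interventional trials by February 2020, and no other ongoing trial is described.
- Sections 2.2.1, 2.2.6 and 2.3 present the agent as sparing marrow. The statement in 2.1.3 is about beta- and alpha-emitters.
- Entry is stricter than the second dose on platelets (100,000 against 75,000/mcL) and hemoglobin (above 10.0 against at least 8.0 g/dL), with the same neutrophil limit.

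A reader might also infer that toxicity from an earlier isotope would be counted as a DLT of the study drug. Section 6.2 places DLTs within 60 days after the second cycle. Read literally, that window opens no earlier than the second dose, when an isotope given 28 days before dose 1 is 28 + 56 = 84 days old. For Sn-117m the remaining activity would be 2^(−84/13.6) = 1.4% to 2^(−84/14) = 1.6%, using the half-lives in 2.3 and 8.1.1 and no biologic clearance from bone (2.2.3.2). The wording of 6.2 is ambiguous, but it does not carry the argument.

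On the hormonal agents, the reply is that patients must already have progressed (3.1.1, 3.1.2), and that Prior Therapies forms (5.4.3.2) and concurrent-drug records (6.3.3) would let affected patients be listed. Both are true. Progression on one agent does not fix when another was stopped, and listing patients does not restore a matched baseline.

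**Conclusion.** The isotope gap holds on the text and is minor. It is a marrow-safety matter for patients who have had a therapeutic isotope outside the five; their share is not given and may be small. Entry counts and toxicity recovery reduce the risk but do not supply the missing interval. This rests on reading the list in 3.2.5 as closed, which is how it is written.

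The hormonal point also holds on the text, as a secondary matter. The documents give neither the size nor the direction of any withdrawal effect.

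A reader might infer that either gap produces false pain responses or raises the type I error of the two-stage rule. The documents give nothing from which to derive such a shift, and no error rate is claimed. For Sn-117m itself, sections 2.2.5 and 2.3 put mean onset of relief at 5 to 22 days, so relief from a dose 28 days earlier would mostly already be in the baseline.

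**What to change.** Reword 3.2.5 to exclude *any therapeutic systemic radioisotope, including but not limited to* the five now named, and keep 24 weeks. The word *therapeutic* leaves the diagnostic scans in 3.1.3 unaffected. The cost is one line in an amendment; a few patients would wait or become ineligible.

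As a second and more optional change, require enzalutamide, apalutamide, darolutamide and abiraterone to be stopped before day 1 of the 7-day diary and before the baseline PSA/ALP draw, leaving androgen deprivation under 3.1.1 untouched. This puts baseline and follow-up on the same footing, but withdrawal effects could still run into follow-up. It also has a real cost: the diary helps decide eligibility (3.1.4), so some patients would stop a drug before knowing whether they qualify. No longer washout is proposed, because the documents give no withdrawal timing for these agents.
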